### **8.7. Discontinuation/Withdrawal of Participants from Trial Treatment**

Each participant has the right to withdraw from the trial at any time. In addition, the Investigator may discontinue a participant from the trial at any time if the Investigator considers it necessary for any reason including:

- Pregnancy
- Ineligibility (either arising during the trial or retrospectively having been overlooked at screening)
- Significant protocol deviation
- Significant non-compliance with treatment regimen or trial requirements
- An adverse event which requires discontinuation of the device or results in inability to continue to comply with trial procedures
- Withdrawal of Consent
- Loss to follow up

No additional procedures or observations will continue to be required after the end of the study.

Withdrawal from the study will result in the exclusion of the data for that participant from analysis.

Withdrawn participants will be replaced by further recruitment to the study.

The reason for withdrawal will be recorded in the CRF.

If the participant is withdrawn due to an adverse event, the investigator will arrange for follow-up visits or telephone calls until the adverse event has resolved or stabilised.

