## **8.1. Recruitment**

The identification of patients suitable for this study will take place at colorectal cancer multi-disciplinary meetings. This will involve reviewing the clinical, histological and radiological investigations with other surgeons, oncologists, radiologists and pathologists as part of the normal clinical review process. The principal investigators, who are part of the standard clinical care team for rectal cancer patients, are routinely present at this meeting.

Identified potential participants will then be approached by the principal investigator during their routine pre-operative clinic visit, and screening will be performed at this time using a checklist. They will be

provided with an information sheet and given time to ask questions. Patients agreeing to participate will be recruited on their subsequent pre-operative visit to the endoscopy unit.

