### **11.3. Procedures for Recording Adverse Events**

All adverse events (including ADEs) and device deficiencies occurring during the course of the study will be recorded on the CRF whether or not attributed to the trial device. The information recorded will include but not be limited to:

- A description of the event
- The dates of the onset and resolution
- Action taken
- Outcome
- Assessment of relatedness to the device
- Whether the AE is serious or not
- Whether the AE arises from device deficiency
- Whether the AE arises from user error

The severity of events will be assessed on the following scale: 1 = mild, 2 = moderate, 3 = severe.

AEs/ADEs considered related to the device as judged by a medically qualified investigator or the Sponsor will be followed either until resolution, or the event is considered stable.

It will be left to the Investigator's clinical judgment to decide whether or not an AE/ADE is of sufficient severity to require the participant's removal from treatment. A participant may also voluntarily withdraw from treatment due to what he or she perceives as an intolerable AE/ADE. If either of these occurs, the participant must undergo an end of trial assessment and be given appropriate care under medical supervision until symptoms cease, or the condition becomes stable.

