## **12. STATISTICS**

### **12.1. Description of Statistical Methods**

All data will be stored in an Excel worksheet and analysed using Excel and R.

Frequency of event (adverse, hypersensitivity or complication) will equate to: number of adverse event/total number of recruited patients.

Frequency of tracer detection at surgery (at tumour site and in lymph nodes) will equate to: number of operations where tracer seen/ total number of operations on recruited patients.

Impact of tracer injection on subsequent surgery will be assessed by the surgeon's binary assessment as to whether surgery was more difficult than expected, and also free text comments to be analysed qualitatively.

A sentinel lymph node will be defined as the first lymph node draining the tumour and positivity defined according to the manufacturer's instructions. A "positive" node will be defined as having over 10% of the tracer activity of the site of initial submucosal injection. A "negative" node will be defined as having less than 10% of the tracer activity of the site of initial submucosal injection.

The detection rate for sentinel lymph nodes on MRI scan and Sentimag probe assessment will equate to: number of patients/specimens in whom a sentinel lymph node is identified/total number of examined patients/specimens.

MRI and Sentimag mapping will be qualitatively compared for all relevant patients/specimens (as appropriate) to establish a baseline of individual variability.

The presence and location of lymph nodes in the mesorectal specimen will be compared with the pathology findings for each patient in the ex-vivo part using correlation.

The success rate for removing the sentinel lymph node during TEM surgery will equate to: number of patients in whom the sentinel lymph node was removed/total number of patients undergoing TEM operation.

As this is a feasibility study, results will be continuously evaluated and adjustments made to the tracer dosage and timing of injection if indicated.

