#### **12.6. Inclusion in Analysis**

All patients who receive the tracer injection will be included in the analysis.

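### Section 8.7 drops withdrawn participants from analysis, including those withdrawn for an adverse event, while Sections 12.6 and 12.1 keep them; applying 8.7 would bias primary endpoint A downward

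*Combined protocol and SAP*

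**What the plan says.** Section 8.7 (Discontinuation/Withdrawal) sets the rule for withdrawn participants: "Withdrawal from the study will result in the exclusion of the data for that participant from analysis". No exception is made for safety data. The listed grounds for discontinuation include "An adverse event which requires discontinuation of the device or results in inability to continue to comply with trial procedures", and the section later arranges follow-up for a participant withdrawn for that reason. It adds: "Withdrawn participants will be replaced by further recruitment to the study". Section 11.3 also foresees such cases: "A participant may also voluntarily withdraw from treatment due to what he or she perceives as an intolerable AE/ADE".

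The Statistics section points the other way:

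- Section 12.6: "All patients who receive the tracer injection will be included in the analysis".
- Section 12.1, for primary endpoint A: "Frequency of event (adverse, hypersensitivity or complication) will equate to: number of adverse event/total number of recruited patients".
- Section 12.1, for tracer detection (endpoint B): "number of operations where tracer seen/ total number of operations on recruited patients".
- Section 12.5 uses all available data and does not impute.

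On when a patient counts as recruited, Section 8.1 says: "Patients agreeing to participate will be recruited on their subsequent pre-operative visit to the endoscopy unit". No section states which rule takes precedence. Section 12.7 treats the reporting of deviations from the statistical plan as not applicable.

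**The concern.** Endpoint A is a primary endpoint, and the documents do not fix its analysis set. Under one of the two written rules, whether a patient is analysed depends on the outcome being measured: a reaction bad enough to end participation takes that patient out of both numerator and denominator. Because the patient is replaced, the analysed number returns to 40, and that number alone would not reveal the exclusion.

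The matter is confined to the reported estimate. Adverse events are still recorded on the CRF (Section 11.3), serious events are still reported (11.4) and reviewed by the Trials Safety Group (11.6), and a participant withdrawn for an adverse event is still followed up (8.7). But Section 4 presents this study as the step before a clinical trial of sentinel node biopsy in rectal cancer. With 40 patients and uncommon reactions, one patient can separate a report of no reactions from a report of a reaction that led to withdrawal.

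**Working it through.** **Plan figures.** The documents give no reaction rate, withdrawal rate, power or significance level for this endpoint, so there is no figure to reproduce. The only number used from the plan is the sample size, 20 ex-vivo + 20 in-vivo = 40 (Section 12.2). All other inputs below are assumptions.

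**Step 1: the rules side by side, for a patient injected, then withdrawn for a reaction.**

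| Rule | Is the patient in endpoint A? |
|---|---|
| 8.7 | No; replaced |
| 12.6 | Yes; was injected |
| 12.1 | Yes; was recruited |
| 12.5 | Yes, for the data available |

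Section 8.7 cannot be followed together with the other three.

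**Step 2: illustrative counts.** Count patients with a tracer reaction. Let x = reactors retained, w = reactors withdrawn after injection, u = non-reactors withdrawn after injection. All withdrawn patients are replaced, so 40 are retained.

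- Under 8.7: x/40.
- Under 12.6: (x + w)/(40 + w + u).

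With u = 0 and exact (Clopper-Pearson) 95% intervals:

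| x | w | Under 8.7 | Under 12.6 |
|---|---|---|---|
| 0 | 1 | 0/40 = 0% (0 to 8.8%) | 1/41 = 2.4% (0.1 to 12.9%) |
| 0 | 3 | 0/40 = 0% (0 to 8.8%) | 3/43 = 7.0% (1.5 to 19.1%) |
| 2 | 1 | 2/40 = 5.0% (0.6 to 16.9%) | 3/41 = 7.3% (1.5 to 19.9%) |

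The first two rows are worst cases, in which every reactor is withdrawn. A mixed reading is also possible, with 8.7 applied to the numerator while the 12.1 denominator keeps everyone recruited. The third row then gives 2/41 = 4.9%.

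**Step 3: expected rate.** Let p = true reaction rate, q = probability that a reactor is withdrawn, r = probability that a non-reactor is withdrawn. The rate among retained patients is

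p(1 − q) / [p(1 − q) + (1 − p)(1 − r)].

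With r = 0 this is p(1 − q)/(1 − pq). It holds however often replacement is repeated, provided the probabilities stay the same. For example, p = 5% and q = 25% give 0.0375/0.9875 = 3.8%.

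| p | q = 25%, r = 0 | q = 50%, r = 0 |
|---|---|---|
| 2% | 1.5% | 1.0% |
| 5% | 3.8% | 2.6% |
| 10% | 7.7% | 5.3% |

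The relative loss is 1 − (1 − q)/(1 − pq): 23 to 25% at q = 25%, and 47 to 50% at q = 50%.

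**Step 4: direction.** The rate falls when q > r, is unchanged when q = r, and rises when q < r. At p = 5%: q = 50% with r = 5% gives 2.7%; q = 0 with r = 5% gives 5.25%. With x = 2 and w = 1, the fall is cancelled when 3/(41 + u) = 2/40, that is, at u = 19 event-free withdrawals after injection.

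**Step 5: the other denominators.** Consent and injection take place at the same endoscopy visit, so someone recruited but not injected counts under 12.1 and not under 12.6. Endpoint B already divides by operations, so 8.7 affects endpoints B and C only if a participant who had surgery is withdrawn, for instance for a protocol deviation.

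**The case against.** The strongest case against is about size and direction. An adverse event is one of seven listed grounds for discontinuation, and exclusion lowers endpoint A only if patients with a reaction withdraw more often than those without. The tracer is given once, so no later dose remains to be stopped, and surgery follows its clinical indication. Section 11.3 speaks of withdrawal from treatment, whereas the exclusion sentence concerns withdrawal from the study. Few patients may therefore be affected. The Statistics section consistently favours inclusion, and there is no hypothesis test or numerical threshold on endpoint A. Section 12.1 also counts events, including complications, so 0/40 is an extreme case under a narrower count. The paired intervals overlap widely.

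Much of this stands as a limit on size: the effect is unknown and may be small, the 25 to 50% range for q has no source in the documents, and the downward direction needs q > r. That condition is nevertheless the one to expect. The other grounds for withdrawal apply to patients with and without a reaction, and an adverse event is an additional ground that applies only to patients who have one. Participation also continues through MRI and surgery until discharge, with surgery about 5 days after injection, so there is time for withdrawal, and Section 8.7 provides for it. The consistency of Section 12 does not settle precedence, because 8.7 is the more specific rule for withdrawn participants. Counting events instead of patients would make the numerator loss larger when an excluded patient had several.

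**Conclusion.** The concern holds. Section 8.7 contradicts Sections 12.6, 12.1 and 12.5 for every participant withdrawn after injection, and the documents give no precedence. If 8.7 is applied, endpoint A is biased downward whenever patients with a reaction withdraw more often than the others.

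The size cannot be derived from the documents. In the assumed examples, one withdrawn reactor moves the estimate by about 2.3 to 2.4 percentage points (5.0% against 7.3%; 0% against 2.4%). The relative loss is close to the share of reactors withdrawn, if nobody else withdraws. These figures count patients with a tracer reaction; if surgical complications are counted as well, the overall frequency would be higher and 0% would not be expected.

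This should be corrected even though the absolute effect may be small, because a written rule removes outcome events from a primary safety endpoint and the repair is simple.

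**What to change.** Delete the exclusion sentence in Section 8.7 and state that:

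1. Data collected up to withdrawal are kept.
2. Every participant who received tracer is in the endpoint A analysis, whether or not withdrawn or replaced, and the Section 12.1 denominator is changed to this injected set.
3. Every injected participant who had surgery stays in the tracer-detection and surgical-impact analyses.
4. Replacements are added to the injected set and do not substitute for anyone in it.
5. Data are removed only where a participant explicitly withdraws consent to their use, and the number of such cases is reported.

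Item 2 repairs endpoint A; item 3 applies the Section 12.6 principle to endpoints B and C.

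The cost is a wording amendment to Sections 8.7 and 12.1, submitted to the sponsor and for any approval needed under Section 16.4, and a check that the participant information (not visible in this copy) agrees. No extra patients or data are needed. The reported reaction frequency may look slightly less favourable. The number analysed may exceed 40, although the number injected could already do so under the existing replacement rule.

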### **8.8. Definition of End of Trial**

The end of trial is the date of the last participant discharged from hospital.

## **9. IDENTIFICATION & DESCRIPTION OF THE INVESTIGATIONAL DEVICE**

### **9.1. Device description**

This study will use Sienna+® or Magtrace® tracer which contains magnetised nanoparticles and a hand-held SentiMag® probe within its CE market intended purpose for sentinel lymph node mapping. Lymph node mapping is used in cancer patients to identify the first lymph nodes that would be affected by spread of the cancer. Specifically, in this study, the device will be used to identify sentinel lymph nodes in the mesorectum of patients with rectal cancer.

The tracer is a dark brown aqueous suspension of organically coated superparamagnetic iron oxide particles, supplied in a vial. It will be diluted and injected during endoscopy. The vials will be supplied directly and will not involve pharmacy.

The manufacturer is Endomagnetics Limited, [name]. The Sienna+ product has been in use since 29 February 2012. On 31 October 2018 Endomagnetics discontinued Sienna+ and replaced it directly with Magtrace, which contains the same nanoparticle, in the same amount and concentration, but formulated in 0.3% saline rather than water.

At the start of the study, the principal investigators will undergo methodology training and practice the use of the hand held SentiMag probe.

### **9.2. Device Safety**

The tracer is supplied in vials with a long shelf life. The storage and handling procedures are straightforward; there are no temperature issues. The vials will be held in a secure storage area in the endoscopy department. The vial details and expiry date will be checked prior to administration in accordance with standard procedures. Details of the batch and injection will be recorded on the standard endoscopy documentation. Details of the injection will also be recorded on the CRF.

The SentiMag includes a probe and a portable base unit that it connects to. There are no safety issues with either the tracer or the probe.

### **9.3. Device Accountability**

The manufacturer (Endomagnetics) is responsible for the quality control of the tracer and probe.

## **10. NON-INVESTIGATIONAL MEDICINAL PRODUCT (NIMP)**

### **10.1. NIMP Description**

Indocyanine green (ICG) dye is a tricarbocyanine dye with a peak spectral absorption in the near infrared (NIR) range. Following injection it can be visualised in the tissues using an NIR imaging system. ICG has a low molecular size so when injected subserosally or submucosally into the bowel it is rapidly taken up by the lymphatics and deposited in the local lymph nodes. It has been widely used for sentinel lymph node mapping in colorectal and other cancers, and is also commonly used as an indicator dye in many other

areas of medicine. ICG contains sodium iodide. It is safe for general use, but can cause allergic reactions in people with iodine sensitivity.

ICG is supplied as a sterile water-soluble powder in 25mg vials. The vials are stored at room temperature. Prior to use the powder is dissolved in 10ml of sterile water. Once dissolved the ICG must be used within 6 hours.

## 11. SAFETY REPORTING

### 11.1. Definitions

Adverse Event (AE)	Any untoward medical occurrence, unintended disease or injury or any untoward clinical signs (including an abnormal laboratory findings) in participants, users or other persons whether or not related to the investigational medical device. This includes events related to the investigational device or comparator, events related to the procedures involved (any procedure in the protocol). For users or other persons this is restricted to events related to the investigational medical device.
Adverse Device effect (ADE)	An adverse event related to the use of an investigational medical device. This definition includes any events resulting from insufficient or inadequate instructions for use, deployment, implantation, installation, or operation, or any malfunction of the investigational device. This definition also includes any event resulting from user error or form intentional misuse of the investigational device.
Serious Adverse Event (SAE)	
An adverse event that:
 
 
• Led to death
 
• Resulted in serious deterioration in the health of the subject that: 
 
○ resulted in a life-threatening illness or injury
 
○ resulted in a permanent impairment of a body structure or a body function
 
○ required in-patient care or prolongation of hospitalisation
 
○ resulted in medical or surgical intervention to prevent life-threatening illness or injury or permanent impairment to a body structure or a body function.
 
 
 
 
This includes device deficiencies that might have led to a serious adverse event if:
 
 
a) suitable action had not been taken or
 

	
b) intervention had not been made or
 
c) circumstances had been less fortunate.
 
These are handled under the SAE reporting system.
 
Planned hospitalisation for a pre-existing condition, or a procedure required by the trial protocol, without serious deterioration in health, is not considered a serious adverse event.

Serious Adverse Device Effect (SADE)	
Any untoward medical occurrence that can be attributed wholly or partly to the device, which resulted in any of the characteristics of a serious adverse event as described above.
 
Unanticipated Serious Adverse Device Effects (USADE)
 
Any serious adverse device effect which, by its nature, incidence, severity or outcome, has not been identified

Device deficiency	
Inadequacy of a medical device with respect to its identity, quality, durability, reliability, safety or performance. Device deficiencies include malfunctions, use errors and inadequate labelling.
 
Device deficiencies that did not lead to an adverse event, but could have led to a medical occurrence if suitable action had not been taken, or intervention had not been made or if circumstances had been less fortunate

User error	
Act or omission of an act that results in a different medical device response than intended by the manufacturer or expected by the user. Use error includes slips, lapses and mistakes. An unexpected physiological response of the subject does not itself constitute a use error.

*Severity definitions*

The following definitions will be used to determine the severity rating for all adverse events:

Mild: awareness of signs or symptoms, that does not interfere with the subject’s usual activity or is transient that resolved without treatment and with no sequelae.

Moderate: a sign or symptom, which interferes with the subject’s usual activity.

Severe: incapacity with inability to do work or perform usual activities.

**11.2. Causality**

The relationship of each adverse event to the trial device may be determined by the manufacturer and/or a medically qualified Investigator according to the following definitions:

**Not related:** The event is clearly related to other factors such as the patients/participants clinical condition, therapeutic intervention, concomitant medication.

**Unlikely:** The event is probably produced by other factors such as the patients/participants clinical condition, therapeutic intervention, concomitant medication and does not follow a known response pattern to the device

**Possibly:** The event follows a reasonable temporal relationship from the time of placement/administration and/or follows a known response pattern to the device but could have been caused by other factors such as the patients/participants clinical condition, therapeutic intervention, concomitant medication.

**Most probable:** The event follows a reasonable temporal relationship from the time of placement/administration and/or follows a known response pattern to the device and could not have been caused by other factors such as the patients/participants clinical condition, therapeutic intervention, concomitant medication. Further the event immediately follows the administration/placement of the device and improves on stopping or removing the device.

### **11.3. Procedures for Recording Adverse Events**

All adverse events (including ADEs) and device deficiencies occurring during the course of the study will be recorded on the CRF whether or not attributed to the trial device. The information recorded will include but not be limited to:

- A description of the event
- The dates of the onset and resolution
- Action taken
- Outcome
- Assessment of relatedness to the device
- Whether the AE is serious or not
- Whether the AE arises from device deficiency
- Whether the AE arises from user error

The severity of events will be assessed on the following scale: 1 = mild, 2 = moderate, 3 = severe.

AEs/ADEs considered related to the device as judged by a medically qualified investigator or the Sponsor will be followed either until resolution, or the event is considered stable.

It will be left to the Investigator's clinical judgment to decide whether or not an AE/ADE is of sufficient severity to require the participant's removal from treatment. A participant may also voluntarily withdraw from treatment due to what he or she perceives as an intolerable AE/ADE. If either of these occurs, the participant must undergo an end of trial assessment and be given appropriate care under medical supervision until symptoms cease, or the condition becomes stable.

